### *Statistical analysis*

Descriptive statistics will be conducted to calculate distributions, frequencies, means and standard deviations for sex, malocclusion, and the results for maximum opening, bite force, inflammation, and pain in each group (experimental and control).

The Kolmogorov-Smirnov test will be applied to check the normality of variable distributions and Levene's test to check the equality of variances.

The Student's t-test will be employed to evaluate the difference in each measurement between experimental and control groups.

The paired Student's t-test will be used to compare measurements before and after TENS/sham-TENS in the same patient.

The GLM repeated-measures procedure will be applied to analyze the results for each group over time.

SPSS 22.0 ® for Windows will be used for statistical analysis

P≤0.05 was considered significant in all tests.

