STUDY PROTOCOL

Use of transcutaneous electrical nerve stimulation (TENS) for the recovery of oral function after orthognathic surgery

NCT ID not yet assigned

05/11/2020

ABSTRACT:

Oral functions of patients are markedly diminished immediately after orthognathic surgery, and novel approaches are needed to accelerate their recovery. The aim of this study will be to examine the usefulness of weekly applications of transcutaneous electrical nerve stimulation (TENS) for this purpose, based on evidence of its effectiveness in other types of patients with muscle alterations. Maximum jaw opening, bite force, pain, and facial inflammation will be compared between patients receiving TENS and those receiving sham-TENS for 30 min at baseline and weekly over a four-week period after orthognathic surgery and will be also compared between before and after each procedure.

MATERIAL

The sample will be made up of a sufficient number of patients according to the calculation of the sample size who will undergo bimaxillary surgery or mandibular surgery divided between experimental (TENS group) and control groups (sham-TENS).

Participants will be selected by non-probabilistic sampling of consecutive patients until the estimated sample size is reached. All patients have a skeletal and facial deformity amenable to surgery after a pre-surgical orthodontic period, and they will have to signed their informed consent after receiving an information sheet on the study.

This study was approved by the ethics committee of the hospital (San Carlos Hospital, Madrid, Spain).

Inclusion criterion:

- programing of bimaxillary or mandibular orthognathic surgery by the same surgeon in order to avoid inter-operator variability.
- no surgery for temporomandibular disorders or more complex syndromes,
- no presence of muscle or nervous disorders or receipt of medication for such disorders

Exclusion criterion:

- the impossibility to attend follow-up appointments
- the refusal of informed consent.

The sample size will be estimated to obtain a statistical power of 80% with an alpha error of 0.05 and 95% confidence interval to detect a difference in jaw opening ≥ 2.5 mm.

Patients will be randomly assigned to the experimental group for TENS application or the control group for sham-TENS and will be blinded to their group assignation, as was the researcher responsible for data analyses (single-blind randomized clinical trial).

METHOD

TENS procedure

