An Enraf Nonius® S82 model TENS device will be used, with a maximum frequency of 220 Hz and an intensity range of 0 to 99.5 mA.

TENS electrodes will be placed bilaterally on mandibular elevator muscles, on the superficial masseter muscle above the gonial angle, and bilaterally on the anterior temporal muscle, following the manufacturer's instructions. The device will be applied in an identical manner to all patients in both groups and kept in position for the same time period (30 min); however, the device will be not switched on for the control group.

The stimulation intensity will be adjusted for those in the experimental group to the maximum that did not cause discomfort or areas of contraction, maintaining this stimulation intensity and frequency throughout the 30-min session.

Each participant will experience a weekly TENS or sham-TENS session on the same day of the week during a four-week period; appointments will be scheduled so as to minimize any possible interaction among study participants.

Study variables

Data will be gathered from all patients on jaw opening, bite force, inflammation, and pain before surgery and at 7, 14, 21, and 28 days post-surgery, conducting measurements both before and after the TENS/sham-TENS session.

Maximum Jaw Opening will be evaluated with patients seated vertically upright in the dental chair, using a digital dental caliber (Model R 100110, Mestra®) to measure the maximum opening from the incisal margin of upper central incisors to the incisal margin of lower incisors, adding the amount (in mm) of overbite or subtracting the amount (in mm) of open bite in occlusion.

Bite force will be measured using Dental Prescale Fuji® film, which is formed by microcapsules that generate a chemical reaction under pressure, staining the contact area with a color density corresponding to the pressure applied.

A sheet of the film will be placed between the occlusal surfaces of the two arches, and the patient will be asked to bite as strongly as possible for 5 sec. This procedure will be repeated three times, selecting the sheet with the best-defined tooth print to be photographed with a Canon® EOS 500 camera (RAW format, F32, and annular Flash) at the minimum distance permitted by the 75-macro lens.

The image will be processed in a Mac® computer to obtain the color value according to the Cie L*a*b* (CIELAB) scale, which gives the color a numerical value.

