The corresponding pressure units (Megapascals, MPa) will be calculated according to Dental Prescale specifications, and the bite force (in Newtons [N]) will be obtained by using the following formula:

$$\text{Bite Force} = \text{Bite Pressure (MPa)} \times \text{mm}^2 \text{ print surface.}$$

Pain perceived by patients while autonomously opening and closing their jaws will be evaluated using a visual analog scale (VAS).

Facial inflammation will be measured (in mm) with patients seated upright in the dental chair, using a soft ruler to obtain a horizontal measurement from the lower border of the earlobe to the corner of the mouth and a vertical measurement from the gonial angle to the outer canthus of the eye. The soft ruler will be adapted to the contour of the patient's face without exerting any pressure.

All of the above measurements provided numeric values for treatment as continuous quantitative variables.

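### Every outcome is measured before surgery, but the between-group t-test ignores those values and the repeated-measures GLM gives them no stated role; specify baseline adjustment, above all for swelling

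*SAP*

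**What the plan says.** Under Study variables, the protocol states: "Data will be gathered from all patients on jaw opening, bite force, inflammation, and pain before surgery". The same measurements follow at 7, 14, 21 and 28 days, "conducting measurements both before and after the TENS/sham-TENS session". Inflammation is recorded as two absolute distances in mm. The first is described as "a horizontal measurement from the lower border of the earlobe to the corner of the mouth". For the second, the protocol specifies "a vertical measurement from the gonial angle to the outer canthus of the eye". No change from the pre-surgery distance is defined.

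The SAP's Statistical analysis section names three procedures.

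- **Between groups:** "The Student's t-test will be employed to evaluate the difference in each measurement between experimental and control groups". No covariate or change score is mentioned.
- **Within patient:** a paired t-test of values before and after a session. This does not refer back to the pre-surgery value.
- **Longitudinal:** "The GLM repeated-measures procedure will be applied to analyze the results for each group over time". No group-by-time term and no covariate are named. The SAP does not say whether the pre-surgery value is a time level, a covariate or left out.

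On allocation, the protocol's Material section says: "Patients will be randomly assigned to the experimental group for TENS application or the control group for sham-TENS".

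**The concern.** In a randomised trial with a pre-treatment measurement of the same variable, the unadjusted comparison of follow-up means is unbiased. It does leave in the error term all the between-patient variation that the pre-surgery value could explain. It also lets any chance difference in baseline pass into the estimate in proportion to the baseline/follow-up correlation.

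Swelling is the clearest case. An earlobe-to-mouth distance on day 7 is the patient's face size plus whatever swelling is present. A group difference in that distance is hard to read as swelling unless it is referred to the same patient's pre-surgery distance. Face size does not bias the comparison, but it can be the larger part of the noise, and a real effect could be missed with data that would have shown it.

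**Working it through.** **Inputs from the documents.** Power 80% and alpha 0.05, for a 2.5 mm difference in jaw opening only (Protocol, Material). No sample size, SD, allocation ratio or correlation is given, so there is no figure of the plan's to reproduce. **Assumptions:** two-sided test, 1:1 allocation, baseline/follow-up correlation rho from 0 to 0.7, and 10 or 20 patients per group.

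**1. Large-sample gain.** ANCOVA multiplies the residual variance by 1 − rho². If the unadjusted test has 80% power, the adjusted power is Phi((1.960 + 0.842)/sqrt(1 − rho²) − 1.960).

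**2. Small-sample gain.** Take the noncentrality that gives the t-test 80% power on N − 2 degrees of freedom, where N is the total. Divide it by sqrt((1 − rho²)(1 + 1/(N − 4))), which allows for expected covariate imbalance, and test on N − 3 degrees of freedom.

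| rho | 1 − rho² | Large sample | 20 per group | 10 per group |
|---|---|---|---|---|
| 0 | 1.00 | 80.0% | 78.9% | 77.3% |
| 0.1 | 0.99 | 80.4% | 79.3% | 77.7% |
| 0.3 | 0.91 | 83.6% | 82.5% | 81.0% |
| 0.5 | 0.75 | 89.9% | 89.0% | 87.8% |
| 0.7 | 0.51 | 97.5% | 97.2% | 96.6% |

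Break-even is rho of about 0.17 at 20 per group and 0.26 at 10 per group. In simulation (20,000 trials per cell; 10, 20 and 30 per group) type I error was 0.046 to 0.052 for both tests, so both are valid.

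**3. Chance imbalance, 20 per group.** One standard error of the baseline difference is sqrt(2/20) = 0.316 SD. At rho 0.5 it moves the unadjusted estimate by 0.5 × 0.316 = 0.158 SD. The effect detectable with 80% power is 0.909 SD, so the shift is 0.158/0.909 = 17% of it.

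**4. Swelling.** Model the follow-up distance as the pre-surgery distance (SD A) plus independent swelling (SD S). Then rho = A/sqrt(A² + S²), and the adjusted variance as a share of the unadjusted is S²/(A² + S²). For assumed A of 5 to 10 mm and S of 2 to 4 mm:

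- A 5, S 4: rho = 5/sqrt(41) = 0.78; share 16/41 = 39%.
- A 7, S 3: rho = 7/sqrt(58) = 0.92; share 9/58 = 16%.
- A 10, S 2: rho = 10/sqrt(104) = 0.98; share 4/104 = 4%.

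At A 7 and S 3 mm, with an assumed 2 mm group difference and 20 per group, power is about 13% unadjusted. Adjusted, it is 56% by the normal approximation and 53% by the small-sample formula of step 2.

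**5. Change score instead of ANCOVA.** With equal variances before and after, a change score has relative variance 2(1 − rho): 1.4, 1.0 and 0.6 at rho 0.3, 0.5 and 0.7. ANCOVA has 0.91, 0.75 and 0.51. Starting from about 80% power, the change score gives about 66% to 67%, 80% and 95% at those correlations. ANCOVA is the safer choice.

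**The case against.** The strongest reply is that the GLM may already use the pre-surgery value. The protocol lists the pre-surgery and the four follow-up measurements as one series, and a repeated-measures GLM over time could include all five. With group as a between-patient factor, the group-by-time term would then compare changes from the patient's own starting point. That reading is possible, but so is a separate within-group model for each arm, and the SAP does not settle it. A pre-surgery time level also differs from covariate adjustment: the group main effect averages in a visit that treatment should not have affected, and the change contrast carries the variance in step 5. So the role of the value is unstated, rather than shown to be absent from the whole plan.

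Three further points stand in part.

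- The t-test is valid under randomisation, so this is a matter of efficiency and interpretation, not of bias.
- Adjustment does not pay everywhere. The protocol expects oral function to fall markedly after surgery, so a strong correlation for jaw opening and bite force cannot be presumed, and pain may gain little if pre-surgery pain is near zero. The loss at rho 0 is about 1 to 3 points of power at these sample sizes.
- Every figure depends on assumed inputs, and the swelling figures on assumed SDs. The true gain in this trial is unknown.

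Part of the SAP was not available for this review, so statements about what is not specified concern the available text.

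**Conclusion.** The point holds. The plan collects a pre-surgery value for every outcome, the only between-group test it names does not use it, and the GLM gives it no stated role. No error in validity is claimed. For jaw opening, bite force and pain the benefit depends on the correlation: from a loss of 1 to 3 points of power at rho 0 to a gain of about 8 to 10 points at rho 0.5, with 10 or 20 per group or a large sample. For swelling the case is stronger, because the outcome is a raw anatomical distance. Under the assumed SDs the correlation is 0.78 to 0.98, well above break-even. The change should be made; it is a low-cost improvement rather than a condition for the trial's validity.

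**What to change.** 1. For each post-surgery measurement, replace the t-test by ANCOVA: outcome on group plus the patient's own pre-surgery value of the same measure. This applies equally to pre-session and post-session readings. For each inflammation distance, use the same landmark distance as covariate.
2. Alternatively, state that the repeated-measures GLM covers the post-surgery visits with group, visit and group-by-visit terms, and the pre-surgery value as covariate.
3. Define the covariate as the pre-surgery reading taken before any TENS or sham session, not the pre-session reading of a later visit. The Abstract places sessions for "30 min at baseline and weekly over a four-week period after orthognathic surgery", while the TENS procedure section describes weekly sessions over four weeks. These passages must be reconciled so that the covariate reading is unambiguous.
4. Present pre-surgery values descriptively by group and do not test them as outcomes.
5. State as a limitation that the vertical distance starts at the gonial angle, which the surgery may itself move. Adjustment removes face size but not skeletal change.

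The cost is SAP wording and about one degree of freedom per covariate. The data are already being collected, and no patients or visits are added.

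### The before/after session analysis is a within-patient paired t-test with no TENS-versus-sham contrast of the change, and the repeated-measures GLM does not state a group or group-by-time term

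*SAP*

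**What the plan says.** The SAP, Statistical analysis, names three inferential procedures.

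- Between arms: "The Student's t-test will be employed to evaluate the difference in each measurement between experimental and control groups".
- Around each session: "The paired Student's t-test will be used to compare measurements before and after TENS/sham-TENS in the same patient".
- Over time: "The GLM repeated-measures procedure will be applied to analyze the results for each group over time".

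One threshold covers them all: "P≤0.05 was considered significant in all tests". None is marked primary, secondary or descriptive.

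The protocol abstract gives the motive for the trial as "novel approaches are needed to accelerate their recovery". It sets out a TENS-versus-sham comparison of the four outcomes and then adds that they "will be also compared between before and after each procedure". Under Study variables, readings are planned pre-operatively and on days 7, 14, 21 and 28 after the operation, with a reading on each side of the session. Under TENS procedure, control patients get the same electrode placement for the same 30 minutes with the device left off. Both arms therefore supply pre- and post-session values.

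**The concern.** The sham arm is there to separate a TENS effect from everything else that can move a reading within 30 minutes: expectation, rest with electrodes in place, practice at opening or biting, and measurement drift. A paired test within patients cannot make that separation, whether it is run in each arm or on all patients together. The SAP analyses the sham patients' changes but never formally contrasts them with the TENS patients' changes.

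The GLM raises a similar question over weeks instead of minutes. All patients are healing after surgery, so a time effect within an arm is expected whether or not TENS works. If the model is fitted to each arm separately, which the sentence allows, its P values describe healing and do not bear on whether TENS speeds it up.

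At stake is how the results will be read. With one P threshold for all tests and no descriptive label, nothing in the visible text stops a significant TENS-arm change beside a non-significant sham-arm change from being taken as a treatment effect.

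**Working it through.** **Inputs.** The documents give alpha 0.05, 80% power and a target difference ("to detect a difference in jaw opening ≥ 2.5 mm"), but no SD, no sample size and no correlations. There is no plan figure to reproduce. Everything below is illustrative: 20 per arm, normal data, two-sided 0.05.

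**1. Paired test when both arms change equally.** Let d be the common true change in SDs of the change. The paired test has noncentrality d√n on n−1 degrees of freedom.

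- d = 0.5, n = 20: 0.5 × √20 = 2.24 on 19 df, so the TENS-arm test is significant with probability 0.56.
- d = 0.3: 0.25. d = 0.2: 0.14.
- Because the arms are independent, TENS significant with sham not significant has probability p(1 − p). At d = 0.5 this is 0.565 × 0.435 = 0.25.
- A paired test pooled over all 40 patients at d = 0.5 is significant in 87% of trials.
- A between-arm t-test of the change, simulated under the same conditions, is significant in 5.1%.

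Over 12 to 40 per arm and d from 0.3 to 0.7, the TENS-arm paired test is significant in 16% to 99% of trials and the discordant pattern occurs in 0.9% to 25%. The between-arm test stays between 4.9% and 5.4%.

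**2. Time effect when TENS does nothing.** Assume four post-surgery visits, healing of 0.2 SD per week and a between-visit correlation of 0.6.

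- Visit means are 0, 0.2, 0.4 and 0.6. The squared deviations from their mean of 0.3 sum to 0.09 + 0.01 + 0.01 + 0.09 = 0.20.
- One arm: λ = n × 0.20/(1 − 0.6) = 20 × 0.20/0.4 = 10. The F test on 3 and 57 df is significant with probability 0.73.
- Both arms in one model: λ = 20 on 3 and 114 df, giving 0.97 for the time effect.
- Group-by-visit in that joint model, by simulation: 5%.

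Even in a joint model, therefore, the time effect is only healing; the group terms carry the treatment question. With healing of 0.1 to 0.4 SD per week and correlation 0.4 to 0.8, the one-arm figure runs from 16% to 100%.

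**3. What the Student's t-test already covers.** Taken with Study variables, "each measurement" plausibly includes both readings at each visit.

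- Pre-session readings at later visits: a between-arm comparison of recovery accumulated before that day's session.
- Post-session reading at the first session: an unbiased between-arm comparison of the immediate effect, though it leaves out the pre-session value.
- Post-session reading at later visits: accumulated recovery and that day's session effect mixed together.

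**4. Gain from adjusting for the pre-surgery value.** For a true difference of 0.8 SD at one visit, the unadjusted t-test has noncentrality 0.8 × √(20/2) = 2.53 on 38 df, which gives 69% power. Adjustment multiplies the residual variance by 1 − ρ², where ρ is the correlation with the pre-surgery value.

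- ρ = 0.6: factor 0.64, noncentrality 2.53/0.80 = 3.16 on 37 df, power 87%.
- ρ = 0.2: factor 0.96, noncentrality 2.53/0.98 = 2.58, power 71%.

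**The case against.** The strongest reply is that the randomised comparison is already planned. The Student's t-test compares the arms on each measurement and, on pre-session readings, addresses accumulated recovery against sham. That stands. A reader might infer that the plan has no TENS-versus-sham test; the text contradicts this.

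Second, a repeated-measures GLM accepts a between-subject factor, and the sentence mentions group and time together, so the authors may well intend a group-by-time analysis. That also stands, which makes the GLM part a request for clarification. It does not touch the paired test, for which no such reading is available.

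Third, a reader might infer that the authors will treat a within-arm P value as proof of efficacy. Nothing says so. The protocol presents the before/after comparison as an additional one, and a common threshold is not an efficacy claim. The plan's weakness is only that it does not rule this use out.

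Fourth, the 56% and 73% figures are powers to detect a real change shared by both arms. They are not false-positive rates: a test that detects healing or a sham response is working properly. They show only that such a result carries no information about TENS versus sham.

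Finally, part of the SAP was not available for this review, so what is not named means not named in the visible text.

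**Conclusion.** The point holds in a limited form. As worded, the before/after session analysis has no between-arm contrast of the change, although the readings for one will be collected in both arms. A significant paired test cannot be attributed to TENS. Under the stated assumptions (20 per arm, equal change of 0.5 SD), a misleading split between arms would appear in about one trial in four. The GLM sentence leaves open whether group enters the model; this may be wording only.

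The trial is not invalidated, because a sound between-arm t-test is planned. The change should be made because it is nearly free and brings the session analysis into line with the sham-controlled design. Confidence is high for what the visible text says. All percentages rest on assumed sample sizes, changes and correlations, and their ranges are wide. The 69% to 87% power gain comes from baseline adjustment, falls to 69% to 71% at a weak correlation, and should not be credited to naming a contrast as such.

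**What to change.** 1. **Session effect.** Compare the post-minus-pre change between TENS and sham. For each outcome, name either one session or the average over sessions as the main comparison, or label all of these tests exploratory. With four outcomes at four sessions there are 16 tests; if independent, the chance of at least one false positive is 1 − 0.95^16 = 56%. List the sessions that count, because the protocol abstract speaks of applications "for 30 min at baseline and weekly over a four-week period after orthognathic surgery".
2. **Recovery course.** State that the GLM is fitted to both arms together with group, visit and group-by-visit, using the pre-session readings. Take the treatment effect from one pre-named between-group contrast adjusted for the pre-surgery value, for example TENS minus sham in jaw opening (the sample-size outcome) at day 28.
3. **Within-arm results.** Report paired tests and time effects as descriptive only.

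The cost is SAP wording and slightly more model specification; the data are unchanged. Within-arm P values would no longer count as evidence of a TENS effect. A single-visit contrast can miss an early effect that has faded, so the visit must be chosen before data are seen. At later sessions the pre-session value may itself reflect earlier sessions, so the change there should be read with that in mind.

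### The before/after question gets 32 to 40 separate session-level tests within arms and no overall answer; one average change per patient, compared once between TENS and sham, would give one more precisely

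*SAP*

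**What the plan says.** The Protocol sets the number of sessions under TENS procedure: "Each participant will experience a weekly TENS or sham-TENS session on the same day of the week during a four-week period". Under Study variables it places the measurements "before surgery and at 7, 14, 21, and 28 days post-surgery, conducting measurements both before and after the TENS/sham-TENS session". The variables are listed there too: "Data will be gathered from all patients on jaw opening, bite force, inflammation, and pain". Inflammation is recorded as two facial distances, one horizontal and one vertical.

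The abstract makes the immediate effect of a session one of its two stated comparisons. Besides the comparison of TENS with sham, the outcomes "will be also compared between before and after each procedure".

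The SAP (Statistical analysis) gives that comparison one sentence: "The paired Student's t-test will be used to compare measurements before and after TENS/sham-TENS in the same patient". The model for repeated data has a different task: "The GLM repeated-measures procedure will be applied to analyze the results for each group over time". The threshold is common to everything: "P≤0.05 was considered significant in all tests". The visible text does not say whether the four sessions are tested one by one, averaged or pooled.

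**The concern.** The immediate effect of a session is a headline question, and every patient supplies four observations of it per variable. A plan that tests each session separately never brings those four observations together. It can miss an effect that is present but modest at every visit. It can also produce significance at, say, two sessions out of four in one arm, with no rule for what that means. The paired test is also a within-arm test, so even a clear result at one session does not say whether the change differs between TENS and sham. At stake are precision and a single interpretable answer, not the validity of the individual tests.

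**Working it through.** **Inputs from the documents.** Four sessions, at days 7, 14, 21 and 28 (Protocol, TENS procedure and Study variables). The abstract's mention of baseline plus weekly application could be read as five; the Method text supports four. Four variables, or five measured quantities if the two facial distances are kept apart. Two arms. A threshold of 0.05 per test, taken as two-sided because the SAP does not say.

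**Inputs not in the documents.** The correlation r between a patient's session changes, the SD and the sample size. I use r = 0.1, 0.3 and 0.5 (adding 0.7 in places) and assume equal variances, a common r and a roughly constant session effect. The plan states no figure on this point, so there is none to reproduce.

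**1. Number of tests, session by session.** 4 variables × 4 sessions × 2 arms = 32. With the facial distances separate, 5 × 4 × 2 = 40.

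**2. Are those tests valid?** Yes. In simulation (40,000 runs; 10, 20 or 30 patients per group) each single-session paired test rejected a true null in 4.7–5.1% of runs. The chance of at least one false positive across the four sessions, for one variable in one arm, was about 18% at r = 0, falling to 13–14% at r = 0.7.

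**3. Precision gained by averaging.** If one session change has variance σ², the mean of four has variance σ²(1+3r)/4. The standard error is therefore multiplied by √((1+3r)/4), within an arm or between arms:

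- r = 0.1: √(1.3/4) = 0.57
- r = 0.3: √(1.9/4) = 0.69
- r = 0.5: √(2.5/4) = 0.79

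**4. Power.** Take a between-arm comparison with 50% power from one session, so that the expected z is 1.96. Power from the mean is Φ(1.96/ratio − 1.96):

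- r = 0.1: Φ(1.48) = 93%
- r = 0.3: Φ(0.88) = 81%
- r = 0.5: Φ(0.52) = 70%

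Starting from 80% power in one session, the mean has about 98%, 94% and 89% at r = 0.3, 0.5 and 0.7. In the other direction, if the mean has 80% power, one session has 49%, 60% and 69% at those values.

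**5. If all pairs were pooled as independent.** The true variance exceeds the assumed one by the factor 1+3r, so the actual error at a nominal 5% is 2(1 − Φ(1.96/√(1+3r))):

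- r = 0: 5.0%
- r = 0.1: 8.6%
- r = 0.3: 15.5%
- r = 0.5: 21.5%

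Simulation with 20 and 40 patients gave 8.6–8.7%, 14.9–16.0% and 21.2–22.1% for the last three. The per-patient mean stayed at 4.8–5.1% for every r simulated (0 to 0.7).

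**The case against.** The strongest reply is that session-by-session testing is a legitimate design. The abstract asks about each procedure, the tests hold their level, and an average over days 7 to 28 of surgical recovery is a different quantity. The gain from averaging also depends on a fairly stable session effect, which the documents neither support nor contradict. All this stands. It is why session results should be kept and why the loss of session-specific inference must be named. It does not supply an overall answer, and the plan has none.

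It can also be said that the repeated-measures GLM might take in both the before and the after values. It could, with session and before/after as within-patient factors. The SAP does not assign it that task, and names the paired t-test for before/after.

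Four stronger readings may tempt a reader and are not supported:

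- That the plan inflates false positives by pooling correlated pairs. No sentence proposes pooling, the abstract points the other way, and inflation needs r > 0. The figures in step 5 are a reason to rule pooling out, not a description of the plan.
- That each test has a quarter of the information. A quarter is right as a count of pairs. Relative to the mean, one session carries (1+3r)/4 of the information: 33%, 48% or 63% at r = 0.1, 0.3 or 0.5.
- That there are exactly 40 tests. The documents list four variables and do not say that the two facial distances are separate endpoints.
- That the SAP never combines sessions. Part of the SAP was not available, so absence can be judged only on the visible text.

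Finally, the power figures concern a between-arm comparison of changes, which the visible SAP does not explicitly plan. They show what the proposed analysis would gain, not the power of the paired test.

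**Conclusion.** The point holds as a matter of efficiency and interpretation. On the best-supported reading, the immediate effect is examined by 32 tests (40 with the facial distances separate), all within arms, each using one of a patient's four changes, with no planned way to read them together. Under a roughly constant session effect and r between 0.1 and 0.5, using all four changes would cut the standard error to 0.57–0.79 of its single-session value. The gain shrinks as r rises and disappears at r = 1. The values of r are assumptions, so the sizes are ranges and not estimates for this trial. The documents do not support a charge of invalid tests or an inflated error rate. This is an inexpensive improvement that should be made before analysis.

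**What to change.** For each variable, make the main before/after analysis one TENS-versus-sham comparison of the average after-minus-before change per patient.

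- If all sessions are attended, use the patient's mean over the four sessions as the single analysis value.
- If some are missed, fit a mixed model to the session changes with arm, session and a patient random effect, and report the average arm difference. The two approaches agree only with complete data: with missed sessions, patient means differ in precision and cover different weeks.
- Report session-by-session changes and an arm-by-session term as descriptive results.
- State that before/after pairs will not be pooled across sessions as if they came from different patients.
- State whether the two facial distances are analysed separately.

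This reduces 32 or 40 tests to four or five comparisons; multiplicity across variables is a separate matter. The cost is a few lines of SAP text and one derived value per variable, with no new data. The downside is that the headline becomes an average over sessions, so an effect confined to one session would be seen only in the descriptive results.
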